Appendix E provides a summary of Sub-Study with statistical rationale.

The following table outlines the general study timelines and milestones, subject to change throughout the duration of the study. A more detailed timeline may be in subsequent documents and plans, i.e., Project Plan.

Table 4: CONFORM Milestones and Timeline

Study Milestones	Forecast
FDA Regulatory Submission	Oct 2021
Regulatory Body approvals	Nov 2021
Central IRB approval	Dec 2021
ClinicalTrials.gov Registration	Dec 2021
First subject enrollment - US	June 2022
First subject enrolled - OUS	Sept 2023
Last subject enrollment	Dec 2026
Last subject last f/u for Primary Safety Endpoint (12 months)	Dec 2027
Last subject last f/u for Primary Efficacy Endpoint (18 months)	June 2028
Last Subject/Last Complete F/U (5 years post)	Dec 2031
Final Data Cleaning and Database Lock	April 2031
Final CSR	July 2031
Study Closure	Dec 2031

8.3 Number of Required Subjects

The sample size requirements for each of the study cohorts:

8.3.1 Roll-in Phase: Up to 300 subjects study-wide may be implanted with the CLAAS Implant as roll-in cases, Investigational sites that implanted 3 subjects with the Initial CLAAS system will be permitted to implant one additional subject with the Next Generation CLAAS System.

Additional investigational sites will be permitted to implant up to a maximum of 3 roll-in subjects (Initial CLAAS System and Next Generation CLAAS System combined). The number of cases is determined through the training and proctoring process and is based upon demonstrated proficiency.

- **8.3.2 RCT Phase**: Up to one thousand six hundred (1600) subjects will be enrolled in the randomized control trial. The sample size is based on the power requirements for the primary effectiveness endpoint and was determined via simulation. With a non-inferiority margin of 3.2%, and one-sided alpha level of 0.025, the sample size of 1600 subjects should provide approximately 85% power for the hypothesis test of non-inferiority accounting for a 10% attrition rate. This sample size is also expected to provide greater than 80% power for the hypothesis test for the primary safety endpoint with a margin of 5.8% and a one-sided 0.025 alpha level. It should be noted that >50%_of the subjects enrolled in the RCT phase will be from the US and no more than 15% of the data will be from one site.
- **8.3.3 Conscious Sedation Single Arm Sub-study:** The sub-study is designed to demonstrate non-inferiority in CLAAS Implant success compared to the CLAAS arm of the RCT based on the 45 Day Endpoint. It is estimated that a total sample size of 130 subjects (including 6% attrition) is required to demonstrate non-inferiority. This estimated sample size will be verified and adjusted,

if necessary, based on the observed rate of CLAAS Implant success rate in the RCT, prior to initiation of the sub-study. Appendix E provides a summary of the Sub-Study with statistical rationale. This Sub-Study will be identified with a separate NCT number from the randomized controlled trial (NCT06049615).

8.4 Estimated Enrollment Time

The trial is anticipated to take approximately 8 years, depending on the rate of enrollment. Enrollment is expected to take approximately 3 years, and each subject will be followed for a total of 5 years. Follow-up visits may occur as part of an expanded access and/or post-approval study, should the CLAAS System gain approval for commercial distribution prior to the subject's 5-year visit.

8.5 Study Endpoints

Study success will be defined as success on both the primary safety and primary effectiveness endpoints.

8.5.1 Primary Safety Endpoint

A composite of:

- Major Procedure-Related Complications including (identified within 12 months of procedure and adjudicated as procedure related):
 - a. cardiac perforation
 - b. pericardial effusion requiring drainage
 - c. ischemic stroke
 - d. device embolization
 - e. major vascular complications
- Major bleeding through 12 months post procedure or
- All-cause death 12 months post procedure

All definitions are provided for all components in Appendix A. All events will be adjudicated by the independent Clinical Events Committee (CEC).

8.5.2 Primary Effectiveness Endpoint

The primary effectiveness endpoint is a composite of ischemic stroke (NeuroARC (29) defined) and systemic embolism through 18 months.

8.5.3 Secondary Endpoints

8.5.3.1 Secondary Safety Endpoints

- 1. All-Cause Mortality (including cardiovascular) through 18 months
- 2. Myocardial infarction evaluated through 7 days post-procedure (See Appendix A for definition)
- 3. Neurologic Events including Stroke (ischemic and hemorrhagic) and TIA including all stroke (See Appendix A for definition)
- 4. Bleeding complications (See Appendix A for definition)
- 5. Vascular complications classified as major/minor and access site/non-access site related (See Appendix A for definition)

6. Device and procedure-related serious adverse events: Summary of all CEC adjudicated adverse events attributed to the device and/or the procedure

8.5.3.2 Secondary Performance and Efficacy Endpoints

(all definitions provided in Appendix A):

- 1. Device Success
- 2. Technical success
- Procedure success
- 4. Embolic Events
- 5. Closure Success at 12 months based upon each of the following criteria:
 - a. demonstration of peri-device leak ≤5 mm
 - b. demonstration of peri-device leak ≤3 mm

8.5.3.3 Secondary Effectiveness Endpoints with Statistical Hypothesis Testing

The following endpoints will have formal statistical hypothesis tests with a gatekeeping approach to control the Type 1 error rate. Each endpoint will be based on a comparison of the treatment and control arms and is described in detail in the Statistical Analysis Plan and Section 12 of the protocol.

- 1. **Non-inferior closure success** (≤5 mm) **at 45 days**, defined as peri-device residual leak ≤5mm by TEE as evaluated by an independent core lab. A 3% margin will be used.
- 2. **Non-inferior closure success** (≤3mm) **at 45-days**, defined as peri-device residual leak ≤3mm on TEE as evaluated by an independent core lab. A 5% margin will be used.
- Non-inferior complete closure success at 45 days, defined as lack of any detectable (>1mm) peri-device residual leak on TEE as evaluated by an independent core lab. A 5% margin will be used.
- 4. **Superior closure success at 45 days**, defined as peri-device residual leak ≤3mm based on TEE as evaluated by an independent core lab.
- 5. Superior closure success at 45 days, device subgroup test: CLAAS vs. specific control device: defined as lack of any detectable (>3mm) peri-device residual leak on TEE as evaluated by an independent core lab. Tests associated with this endpoint will be performed in descending order of specific control devices (device testing will be performed only for control devices that are used >20% of cases).
- 6. **Superior complete closure success at 45 days**, defined as lack of any detectable (>3mm) peri-device residual leak on TEE as evaluated by an independent core lab.
- 7. Superior closure success at 45 days, device subgroup test: CLAAS vs. specific control device: defined as lack of any detectable (>1mm) peri-device residual leak on TEE as evaluated by an independent core lab. Tests associated with this endpoint will be performed in descending order of specific control devices (device testing will be performed only for control devices that are used >20% of cases).

8.6 Subject Selection

8.6.1 Subject Population

The subject population from which subjects for this trial will be recruited consists of adult subjects presenting with non-valvular atrial fibrillation who are at increased risk for stroke and systemic

embolism based on CHADS₂ or CHA₂DS₂-VASc scores, and who are recommended for oral anticoagulation therapy but have an appropriate rationale to seek a non-pharmacologic alternative to long-term oral anticoagulation, and who have been deemed appropriate for LAA closure by the site investigator and a clinician not a part of the procedural team, using a shared decision process in accordance with standard of care.

8.6.1.1 Enrollment of Medicare Beneficiaries

This study eligibility criteria includes subjects that are largely identified in the Medicare population. As such, the randomized trial design is considered adequate to characterize the safety and effectiveness of the CLAAS system and will appropriately support the CMS criterion for coverage.

8.6.1.2 Enrollment/Representation of Underrepresented Demographic Subgroups

Historically, specific demographic subgroups such as women and racial or ethnic minorities have been under-represented or excluded from many clinical trials, leading to a lack of information on these subgroups for many medical treatments. Certain medical products elicit different responses in specific demographic subgroups. Therefore, it is important to ensure there is an adequate representation of such demographic subgroups and to assess whether there is a different response between different demographic subgroups.

Conformal will work to ensure adequate representation and retention of women and racial or ethnic minorities in this trial. The population in this trial is expected to be older; therefore, some of the traditional reasons for low participation of women are unlikely to affect the CONFORM Pivotal Trial (e.g., fear of fetal injury, family responsibilities). The Statistical Analysis Plan includes analyses to assess heterogeneity of safety and effectiveness endpoints across demographic subgroups.

8.6.2 Eligibility Criteria

8.6.2.1 Inclusion Criteria

Potential subjects must meet **ALL** of the following criteria to be eligible for enrollment into the study:

8.6.2.1.1 General Inclusion Criteria

- 1. Male or non-pregnant female aged ≥18 years.
- 2. Documented non-valvular AF (paroxysmal, persistent, or permanent).
- 3. High risk of stroke or systemic embolism, defined as CHA2DS2-VASc score of ≥3.
- 4. Has an appropriate rationale to seek a non-pharmacologic alternative to long-term oral anticoagulation.
- 5. Deemed by investigator to be suitable for short term oral anticoagulation therapy but deemed less favorable for long-term oral anticoagulation therapy.
- Deemed appropriate for LAA closure by the site investigator and a clinician not a part of the procedural team using a shared decision-making process in accordance with standard of care.
- 7. Able to comply with the protocol-specified medication regimen and follow-up evaluations.
- 8. The subject (or legally authorized representative, where allowed) has been informed of the nature of the study, agrees to its provisions, and has provided written informed consent approved by the appropriate institutional review board (IRB)/Regional Ethics Board (REB)/Ethics Committee (EC).

8.6.2.2 Exclusion Criteria

Potential subjects will be excluded if **ANY** of the following criteria apply:

8.6.2.2.1 General Exclusion Criteria

- 1. Pregnant or nursing subjects and those who plan pregnancy in the period up to one year following the index procedure. Female subjects of childbearing potential must have a negative pregnancy test (per site standard test) within 7 days prior to index procedure.
- Anatomic conditions that would prevent performance of an LAA occlusion procedure (e.g., atrial septal defect (ASD) requiring closure, high-risk patent foramen ovale (PFO) requiring closure, a highly mobile inter-atrial septal aneurysm precluding a safe TSP, presence of a PFO/ASD closure device, history of surgical ASD repair or history of surgical LAAO closure).
- 3. Atrial fibrillation that is defined by a single occurrence or that is transient or reversible (e.g., secondary thyroid disorders, acute alcohol intoxication, trauma, recent major surgical procedures).
- 4. A medical condition (other than atrial fibrillation) that mandates long-term oral anticoagulation (e.g., history of unprovoked deep vein thrombosis or pulmonary embolism, or prosthetic mechanical heart valve).
- 5. History of bleeding diathesis or coagulopathy, or subjects in whom antiplatelet and/or anticoagulant therapy is contraindicated.
- 6. Documented active systemic infection.
- 7. Symptomatic carotid artery disease (defined as >50% stenosis with symptoms of ipsilateral transient or visual TIA evidenced by amaurosis fugax, ipsilateral hemispheric TIAs or ipsilateral stroke); if subject has a history of carotid stent or endarterectomy the subject is eligible if there is <50% stenosis noted at the site of prior treatment.
- 8. Recent (within 30 days of index procedure) or planned (within 60 days post-procedure) cardiac or major non-cardiac interventional or surgical procedure.
- 9. Recent (within 30 days of index procedure) stroke or transient ischemic attack.
- 10. Recent (within 30 days of index procedure) myocardial infarction.
- 11. Vascular access precluding delivery of implant with catheter-based system.
- 12. Severe heart failure (New York Heart Association Class IV).
- 13. Prior cardiac transplant, history of mitral valve replacement or transcatheter mitral valve intervention, or any prosthetic mechanical valve implant.
- 14. Renal insufficiency, defined as estimated glomerular filtration rate (eGFR) <30mL/min/1.73 m2 (by the Modification of Diet in Renal Disease equation).
- 15. Platelet count <75,000 cells/mm3 or >700,000 cells/mm3, or white blood cell count <3,000 cells/mm3.
- 16. Known allergy, hypersensitivity or contraindication to aspirin, heparin, or device materials (e.g., nickel, titanium) that would preclude any P2Y12 inhibitor therapy, or the subject has contrast sensitivity that cannot be adequately pre-medicated.
- 17. Actively enrolled or plans to enroll in a concurrent clinical study in which the active treatment arm may confound the results of this trial.

- 18. Unable to undergo general anesthesia.
- 19. Known other medical illness or known history of substance abuse that may cause non-compliance with the protocol or protocol-specified medication regimen, confound the data interpretation, or is associated with a life expectancy of less than 5 years.
- 20. A condition which precludes adequate transesophageal echocardiographic (TEE) assessment.

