- 15. Platelet count <75,000 cells/mm3 or >700,000 cells/mm3, or white blood cell count <3,000 cells/mm3.
- 16. Known allergy, hypersensitivity or contraindication to aspirin, heparin, or device materials (e.g., nickel, titanium) that would preclude any P2Y12 inhibitor therapy, or the patient has contrast sensitivity that cannot be adequately pre-medicated.
- 17. Actively enrolled or plans to enroll in a concurrent clinical study in which the active treatment arm may confound the results of this trial.

- 18. Unable to undergo general anesthesia.
- 19. Known other medical illness or known history of substance abuse that may cause non-compliance with the protocol or protocol-specified medication regimen, confound the data interpretation, or is associated with a life expectancy of less than 5 years.
- 20. A condition which precludes adequate transesophageal echocardiographic (TEE) assessment.

Echocardiographic Exclusion Criteria

- Left atrial appendage anatomy which cannot accommodate a commercially available control device or the CLAAS Implant per manufacturer IFU (e.g., the anatomy and sizing must be appropriate for both the investigational (CLAAS) and a commercially available device to be enrolled in the trial).
- 2. Intracardiac thrombus or dense spontaneous echo contrast consistent with thrombus, as visualized by TEE prior to implant.
- 3. Left ventricular ejection fraction (LVEF) <30%.
- 4. Moderate or large pericardial effusion >10 mm or symptomatic pericardial effusion, signs or symptoms of acute or chronic pericarditis, or evidence of tamponade physiology
- 5. Atrial septal defect that warrants closure.
- 6. High risk patent foramen ovale (PFO), defined as an atrial septal aneurysm (excursion >15 mm or length >15 mm) or large shunt (early [within 3 beats] and/or substantial passage of bubbles, e.g., ≥20).
- 7. Moderate or severe mitral valve stenosis (mitral valve area <1.5cm²).
- 8. Complex atheroma with mobile plaque of the descending aorta and/or aortic arch.
- 9. Evidence of cardiac tumor.

Follow-up Requirements

Follow-up visits will occur prior to hospital discharge and at 7 days via telehealth assessment and at 45 days (imaging and telehealth), 6 months (telehealth visit), 12 months (imaging and telehealth) and 18 months (clinic visit), and 2, 3, 4 and 5 years (telehealth) post procedure.

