A second-generation WATCHMAN Device, the WATCHMAN FLXTM, was developed to simplify LAAO and was studied in the Pinnacle Study, a single arm study which showed comparable performance.. (21) Based on the Pinnacle study results, the WATCHMAN FLX received FDA approval in July 2020.(22) Recently, Abbott Laboratories (Abbott Park, IL) received FDA Approval for the Amplatzer Amulet Left

Atrial Appendage Occluder.(23) The Amulet consists of a lobe and disk connected by a flexible waist and is constructed from a nitinol mesh and a polyester patch. The Amulet is deployed using a similar procedure as the WATCHMAN and comes in 8 sizes..(24)

While LAA closure with the WATCHMAN and Amplatzer devices represents an important advance in stroke prevention for patients with AF, important limitations remain. These include the need for precise measurement of LAA diameter and depth, precision coaxial delivery, frequent residual leaks and anatomic features which make LAAO difficult to achieve.

The stroke risk for patients with AF has been extensively studied. The Swede Afib study examined the stroke risk in 180,000 untreated AF patients from 2005-2008 and further validated the CHA₂DS₂-VASc as seen in the figure below.(25)

[figure not shown]

Figure 1: Extracted from European Heart Journal (2012) 33, 1500-1510(25)

These data have allowed prediction of the rate of strokes for subjects enrolled in the CONFORM Trial if untreated medically or without LAAO. Assuming a CHA₂DS₂-VASc score of 4.5 (the observed score reported for subjects recruited to the AMULET(26) and Pinnacle Trials(21)) the stroke risk is ~6% per year based upon the Swede Study. We expect the stroke risk to be similar in subjects who are enrolled in the CONFORM Trial. The poor acceptance of OAC was also highlighted by the Swedish study which showed that >45% of subjects with indication for OAC (CHA2DS2-VASc ≥2) were untreated. These data underscore the need for alternatives to traditional pharmacologic treatment such as LAAO. Presently, there are only two LAAO implantable devices available which have the limitations listed above. Therefore, additional options for patients and caregivers are needed.

Conformal Medical, Inc (Nashua, NH), the CONFORM study sponsor, has developed the CLAAS System to address these limitations of the first generation LAAO devices. Early experiences with the CLAAS System have been published (27, 28) and an updated brief summary of the studies are provided below.

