7.4.1.2 CLAAS Implant

The CLAAS Implant is designed to conform to the geometry of the LAA and is delivered via a percutaneous Delivery System. The implant is designed to permanently seal off the LAA from the LA with an endothelial layer that forms across the LA face of the implant. The implant is available in two different sizes; Regular (27 mm) and Large (35 mm) to accommodate patient anatomy. Angiography and/or echocardiography at the time of the procedure may be used to determine the LAA ostium diameter to properly select the Implant size (Table 1). The implant has an inner, cylindrical, Nitinol endoskeleton (frame) that provides the mechanical base structure (#4 in Figure 3). The Nitinol endoskeleton contains 10 face struts and 20 anchors (Regular size) and 12 struts and 24 anchors (Large size) facing proximally to engage the tissue to resist movement. The endoskeleton also provides the conformable structure to enable the foam cylinder (#2 in Figure 3) to compress against the LAA tissue to facilitate sealing.

CLAAS Implant

- 1. ePTFE Outer Cover thromboresistant surface
- 2. Foam Body
- 3. Foam Bumper 5mm height
- 4. Endoskeleton
- 5. Anchors 2 rows; 10/row for Regular 27mm CLAAS or 12/row for Large 35mm CLAAS
- 6. Bumper Markers (x4 within the Bumper)
- 7. Shoulder Marker (for placement reference)
- 8. Tether
- 9. Tether Pin

Figure 3: CLAAS Implant Components

Table 1: CLAAS Implant sizing

Implant Size	Mean LAA Ostium Diameter (D _{max} + D _{min}) / 2	LAA Ostium Diameter Range	Minimum Landing Zone Depth
Regular	≤ 25 mm	10 – 33 mm	10 mm
Large	≤ 32 mm	20 – 40 mm	10 mm

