8.6.2.2.2 Echocardiographic Exclusion Criteria

- 1. Left atrial appendage anatomy which cannot accommodate a commercially available control device or the CLAAS Implant per manufacturer IFU (e.g., the anatomy and sizing must be appropriate for both the investigational (CLAAS) and a commercially available device in order to be enrolled in the trial).
- 2. Intracardiac thrombus or dense spontaneous echo contrast consistent with thrombus, as visualized by TEE prior to implant.
- 3. Left ventricular ejection fraction (LVEF) <30%.
- 4. Moderate or large pericardial effusion >10mm or symptomatic pericardial effusion, signs or symptoms of acute or chronic pericarditis, or evidence of tamponade physiology.
- 5. Atrial septal defect that warrants closure.
- 6. High risk patent foramen ovale (PFO), defined as an atrial septal aneurysm (excursion >15mm or length >15mm) or large shunt (early [within 3 beats] and/or substantial passage of bubbles, e.g., ≥20).
- 7. Moderate or severe mitral valve stenosis (mitral valve area <1.5cm²).
- 8. Complex atheroma with mobile plague of the descending aorta and/or aortic arch.
- 9. Evidence of cardiac tumor.

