9.5.4 Intraprocedural Medical Therapy

Intraprocedural anticoagulation with heparin should be administered per physician standard practice in accordance with published guidelines and local standards of care, with a goal of maintaining an activated clotting time (ACT) of 250-350 sec throughout the procedure. The highest and lowest intraprocedural ACT measurements shall be recorded in the CRF for all subjects.

Total heparin dose and prophylactic antibiotics shall be recorded in the subject's medical record and recorded on the eCRF.

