9.6 Anticoagulation/Antiplatelet Therapy Requirements – CLAAS

9.6.1 Post-Procedure

- If the final **post procedural**, post tether release TEE demonstrates adequate seal (residual leak ≤5mm) and there is no evidence of thrombus, subjects *shall* receive DAPT (ASA 81-100 mg QD and clopidogrel* 75 mg QD) until 45 days post-procedure imaging.
- At **45 days**, if adequate closure has been documented on imaging, DAPT *should* be continued to 6 months, unless deemed unsafe by the subject's physician.
- At **6 months**, if adequate closure has been documented on the 45-day TEE, DAPT should be replaced by monotherapy (ASA 81-100 mg preferred, P2Y12 inhibitor permitted) until 12-month clinical assessment; and is recommended for the duration of the trial (clopidogrel* may be substituted for ASA at the discretion of the subject's physician).
- At **12 months**, if adequate closure has been documented on imaging, medical therapy should be administered based upon institutional standard of care.

NOTE: A substitute P2Y12 inhibitor (i.e., prasugrel, ticagrelor) may be used as per managing physician's judgement. For subjects who are known clopidogrel non-responder an alternative P2Y12 inhibitor should be used.

9.6.2 Additional Considerations:

Inadequate seal: Subjects with inadequate seal (residual leak >5mm) at the post-deployment TEE (or any subsequent TEE or Cardiac CT) should be evaluated for treatment with DOAC and ASA for 4-6 weeks followed by repeat TEE. If inadequate seal persists on TEE, antithrombotic therapy should be considered until seal is confirmed on follow up imaging. Repeat imaging should

be conducted per SOC. Resolution of inadequate seal must be documented on follow up imaging. All additional SOC imaging (TEE or Cardiac CT) should be provided to the Sponsor for Core Lab Review. Antithrombotic therapy should be individualized to the subject based on anatomic (size of leak) and clinical (risk of anticoagulation) considerations.

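### Exclusion 16 ties device-material allergy (nickel, titanium) to P2Y12 inhibitor use, so as written no listed criterion excludes that allergy on its own

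*Protocol*

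**What the plan says.** Protocol Section 8.6.2.2.1, General Exclusion Criteria, no. 16 opens: "Known allergy, hypersensitivity or contraindication to aspirin, heparin, or device materials (e.g., nickel, titanium) that would preclude any P2Y12 inhibitor therapy". A further limb on contrast sensitivity follows. The synopsis (Section 4) has the same construction: "device materials (e.g., nickel, titanium) that would preclude any P2Y12 inhibitor therapy, or the patient has contrast sensitivity".

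On materials, Section 7.4.1.2 says of CLAAS: "The implant has an inner, cylindrical, Nitinol endoskeleton (frame) that provides the mechanical base structure". Section 6.2 describes the WATCHMAN control as a nitinol structure and says that the Amulet "is constructed from a nitinol mesh and a polyester patch".

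On the drugs involved, Section 9.5.4 states: "Intraprocedural anticoagulation with heparin should be administered per physician standard practice". Under Section 9.6.1, CLAAS subjects with adequate seal and no thrombus are to "receive DAPT (ASA 81-100 mg QD and clopidogrel* 75 mg QD) until 45 days post-procedure imaging".

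Appendix E applies the same inclusion and exclusion criteria to the conscious sedation sub-study.

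**The concern.** By naming nickel and titanium, the criterion shows that its authors regarded allergy to the implant's materials as relevant to eligibility. The sentence then makes that allergy count only if it prevents use of a P2Y12 inhibitor. That is a question about a drug, and a metal allergy would not be expected to bear on it. Separate exclusions seem to have been run together, and the device-material limb has lost its effect.

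At stake is a safety criterion that, followed to the letter, gives a result its authors probably did not intend, for a permanent implant. It also leaves monitors without a settled rule. Section 11 makes enrolment of a subject who met an exclusion a protocol deviation, yet for a patient with known nickel allergy the text does not clearly say whether one was met.

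**Working it through.** There is no figure to reproduce and no arithmetic applies. The check has two parts: how the sentence parses, and whether another criterion fills the gap.

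**Step 1: the two possible attachments of the P2Y12 condition.**

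| Limb of no. 16 | Reading A: condition governs the whole list | Reading B: condition governs the last item only |
|---|---|---|
| Aspirin | conditional | excludes on its own |
| Heparin | conditional | excludes on its own |
| Device materials | conditional | conditional |
| Contrast sensitivity | separate limb | separate limb |

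The device-material row is the same under both readings. No comma or conjunction parts the bracketed metals from the condition. The contrast limb, by comparison, is introduced by a comma, a conjunction and a new subject, so the sentence does mark an independent limb where one was meant.

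**Step 2: can the device-material limb ever operate?** It does so only for an allergy to a device material that also rules out every P2Y12 inhibitor or, on another sense of the wording, at least one. On the assumption that a metal allergy has no bearing on P2Y12 use, the limb excludes nobody.

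**Step 3: does another criterion fill the gap?**
- Exclusion 5 is about drugs: "History of bleeding diathesis or coagulopathy, or subjects in whom antiplatelet and/or anticoagulant therapy is contraindicated".
- Exclusion 19 concerns illness or substance abuse affecting compliance, interpretation or life expectancy.
- Echocardiographic exclusion 1 refers to the IFU, but only for anatomy and sizing: "Left atrial appendage anatomy which cannot accommodate a commercially available control device or the CLAAS Implant per manufacturer IFU".
- Inclusion 6 asks for a general judgement that appendage closure is appropriate and does not mention materials.
- Inclusion 7 concerns ability to follow the medication regimen and attend follow-up.

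None names material allergy.

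**Step 4: the same test for the drug limbs.** Aspirin and heparin allergy are conditional only under Reading A. Even then, exclusion 5 removes patients with a contraindication to antiplatelet or anticoagulant therapy, and inclusion 7 removes those who cannot take the required regimen. P2Y12 inhibitors are antiplatelet agents, so the same two criteria reach intolerance of them. The gap that remains is device materials.

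**Step 5: reach.** The wording governs up to 300 roll-in and 1600 randomised subjects (Section 8.3) and, through Appendix E, the estimated 130 sub-study subjects. These are cohort sizes, not counts of affected patients.

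**The case against.** The strongest reply is that nobody would apply the sentence literally. Naming nickel and titanium signals an intent to exclude, and the literal reading makes those words pointless. Other safeguards also exist:
- Inclusion 6 requires the site investigator and a clinician outside the procedural team to judge the patient appropriate.
- Section 9.5.8 calls for implantation per the manufacturer's IFU, and Section 12.3 classes use contrary to the IFU as device misuse.
- Section 9.3 anticipates a sponsor review of eligibility for the first five cases at sites without appropriate prior CLAAS experience.

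Much of this stands, and it rules out four stronger conclusions that a reader might draw:
- **That a nickel-allergic patient is eligible.** The text supports only that no written criterion excludes such a patient. Judgement or the IFU may do so, and the IFU is not available to check.
- **That aspirin- or heparin-allergic patients are let in.** This needs Reading A, and exclusion 5 and inclusion 7 largely cover those patients anyway.
- **That P2Y12 intolerance is overlooked.** The same two criteria reach it, and Section 9.6.1 allows a substitute P2Y12 inhibitor.
- **That sites enrol different populations, or that the comparison is biased.** Nothing in the protocol shows that sites read no. 16 differently. Randomisation is stratified by site, and the WATCHMAN and Amulet controls are also described as nitinol.

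The reply does not repair the criterion. A safety exclusion should not depend on sites setting its words aside, and none of the safeguards mentions material allergy in the text at hand.

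**Conclusion.** The point holds for device materials. Under either parsing, exclusion 16 makes a known nickel or titanium allergy exclusionary only through an unrelated drug condition, and no other listed criterion excludes it. For aspirin and heparin the scope is ambiguous but of little practical consequence.

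This is a drafting error in operative eligibility text, relevant to safety and readily corrected; it is not a design choice. It has no effect on the primary analyses, the margins, power or type I error. The number of patients affected cannot be estimated, because the protocol gives no prevalence of metal allergy.

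The conclusion rests on two assumptions: that a metal allergy does not bear on P2Y12 inhibitor use, and that the sponsor meant material allergy to count in its own right. The second is likely from the wording, but only the sponsor can confirm it.

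**What to change.** Reword no. 16 identically in the synopsis (Section 4) and Section 8.6.2.2.1. The device-material limb should be grammatically separate from the P2Y12 condition. Each limb (aspirin and heparin, device materials, P2Y12 inhibitors, contrast) should state whether it excludes on its own. The sponsor's clinical leads should confirm the intended scope of each limb; this review does not propose a clinical rule for any of the allergies. The eligibility CRF should be aligned with the new text. Because Appendix E adopts the RCT criteria by reference, the correction carries into the sub-study. Its pointer to Section 8.5 should be corrected at the same time, since the criteria stand in Section 8.6.

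The cost is a small protocol amendment, with IRB/REB/EC approval and any regulatory submission that Sections 18.2 and 18.5 require. That review would span up to 120 sites (100 in North America, 5 in Japan and 15 in the EU/EEA and Central Asia). There may also be a few more screen failures.
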